# **2. INTRODUCTION**

This SAP provides the detailed methodology for summary and statistical analyses of the data collected in study C3711001. This document may modify the plans outlined in the protocol; however, any major modifications of the primary endpoint definition or its analysis will also be reflected in a protocol amendment.

# 2.1. Study Objectives

The study objectives are shown below along with their corresponding endpoints.

Primary Objective(s):	Primary Endpoint(s):
To determine the effect of co-administration of PF-05221304 and PF-06865571 on whole liver fat compared to placebo, PF-05221304 administered alone, and PF-06865571 administered alone in subjects with non- alcohlic fatty liver disease (NAFLD).	Relative change from Baseline in whole liver fat at Day 42, as assessed by magnetic resonance imaging proton density fat fraction (MRI-PDFF).
Secondary Objective(s):	Secondary Endpoint(s):
To evaluate safety and tolerability of PF- 05221304 and PF-06865571 co-administration compared to placebo, PF-05221304 administered alone, and PF-06865571 administered alone in subjects with NAFLD.	Assessment of treatment-emergent adverse events (and serious adverse events), clinical laboratory tests including lipids, vital signs, and 12-lead electrocardiograms (ECGs).

Tertiary/Exploratory Objective(s):	Tertiary/Exploratory Endpoint(s):
To evaluate the effect of co-administration of PF-05221304 and PF-06865571, on liver function tests (LFTs) compared to placebo, PF- 05221304 administered alone, and PF- 06865571 administered alone in subjects with NAFLD.	
 
Percent change from Baseline at all time points for:
 
Alanine aminotransferase (ALT), Aspartate aminotransferase (AST).
 
Alkaline Phosphatase.
 
Gamma-glutamyl transferase (GGT).
 

To evaluate effects of co-administration of PF- 05221304 and PF-06865571 on lipids compared to placebo, PF-05221304 administered alone, and PF-06865571 administered alone in subjects with NAFLD.	
 
Percent change from Baseline at all time points for:
 
Triglycerides.
 
Total cholesterol, HDL-C, direct LDL-C, Total cholesterol/HDL-C ratio, and non- HDL-C.
 

CCI	
To evaluate the PD effects of co-administration of PF-05221304 and PF-06865571 compared to placebo, PF-05221304 administered alone, and PF-06865571 administered alone, in adults with NAFLD.	Analyses for PD parameters: % Change from Baseline to Day 42 in Apolipoproteins (A1, B100 and C3). % Change from Baseline to Day 42 in plasma proprotein convertase subtilisin/kexin type 9 (PCSK9)
Pa	ge 6

CCI

CCI		
To collect banked biospecimen for research, unless prohibited by loca or ethics committee decision.	exploratory l regulation	Collection of banked bio-specimens unless prohibited by local regulations or ethics committee decision. Additional information on collection and potential use is provided in Section 7.7 of the Protocol

# 2.2. Study Design

This is a randomized, double blind (sponsor open), placebo-controlled, 2x2 factorial, 4 arm (placebo, monotherapy of PF-05221304, monotherapy of PF-06865571 and combination of PF-05221304 and PF-06865571), parallel group study (Figure 1).

# Figure 1. C3711001 Study Design

Determination of eligibility for this study will occur via a sequential, 3 step process, starting at the first screening visit (Screen 1). Subjects identified to be eligible based on Screen 1 AND Screen 2 procedures will proceed to Screen 3 to measure liver fat by MRI-PDFF. For a given subject, this three-step eligibility assessment may take up to 6 weeks.

Once confirmed to be eligible based on results of Screen 3, subjects will progress to a Run in period (Visit 4), at which time subjects will receive single blind placebo for approximately 14 days to ensure compliance with the administration of investigational product (IP). Approximately 4 days prior to randomization, subjects will report to the imaging center (Visit 5) to have a Baseline MRI PDFF scan performed. At Visit 6 (Day 1), subjects will be

randomized to receive 1 of 4 blinded IP regimens (placebo, PF-05221304 monotherapy, PF-06865571 monotherapy, or PF-05221304 plus PF-06865571 combination) for a duration of up to 6 weeks (ie, 42 days). This study includes a total of 11 scheduled outpatient visits to the study site, including 4 visits to the imaging center, and a safety Follow up telephone contact. The total participation, from Visit 1 (Screen 1) to Follow up telephone phone call will be up to approximately 19 weeks.

Approximately 98 subjects (14 for the placebo group, 28 for each of the monotherapy groups and 28 for the combination group) will be randomized at approximately 30 sites (refer to Section 9.1 of the Protocol).

Subjects who are noted to have non evaluable Baseline MRI-PDFF, as determined by the sponsor identified central imaging vendor, should have their MRI-PDFF repeated once; if the images are still non evaluable on single repeat, the subject will be considered as screen failed; otherwise, there are no plans to replace subjects who are prematurely withdrawn.

# **3. ENDPOINTS AND BASELINE VARIABLES: DEFINITIONS AND CONVENTIONS**

# **3.1. Primary Endpoint(s)**

Relative change from Baseline (CBL) (ie, observed value / Baseline value) in whole liver fat at Day 42, as assessed by MRI-PDFF. Baseline is defined as the planned measurement collected closest *prior to* dosing on Day 1.

The liver fat or the whole liver PDFF is calculated from the pre-defined individual segmental PDFFs labeled Segment I, II, III, IVa, IVb, V, VI, VII and VIII as follows:

Whole Liver PDFF = PDFFs for (Segment I + Segment II + Segment III + Segment IVa + Segment IVb + Segment V + Segment VI + Segment VII + Segment VIII) / (number of segments assessed).

A minimum of 5 non-missing common segments is needed in order to calculate whole liver PDFF. All segments are equally weighted.

While deriving the relative CBL, the same segments are to be used at both Baseline and post-Baseline time points in the calculation of whole liver PDFF. For example, if at Baseline PDFFs from all segments are available but, on Day 42, only 7 segments have non-missing results, whole liver PDFF will be calculated using the matching individual segmental PDFFs at *both* Baseline and Day 42.

## 3.2. Secondary Endpoints

• The secondary endpoints include the standard safety endpoints, namely, adverse events (AEs), serious adverse events (SAEs), clinical laboratory tests including lipids,

vital signs (including blood pressure and pulse rate), and 12-lead ECGs. These will be further described in Section 3.5.

- **3.3.** Tertiary/Exploratory **Endpoints** 
  - % CBL at all time points for ALT, AST, Alkaline Phosphatase, Gamma glutamyl transferase (GGT).
  - % CBL at all time points for triglycerides, total cholesterol, HDL-C, direct LDL-C, total cholesterol/HDL-C ratio, and non-HDL-C

Baseline is defined as the result closest *prior to* dosing on Day 1. The parameter of non-HDL-C will be calculated as follows:

C C I	
-	
_	
•	PD Parameters:
	- % CBL to Day 42 in Apolipoproteins (A1, B100 and C3).
	Page 9
	CCI

Non-HDL-C = Total cholesterol - HDL-C

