Confirm contraceptive method	Х			Х		Х	Х	Х	Х	Х	Х		
Instructions on Dosing of IP				Х		Х	Х	Х	Х				
Counseling on diet/exercise guidelines				Х		Х		Х	Х	Х	Х		
Blood Collections after ≥8-hour, preferably 10-ho	ur fast; refer	to Table '	7 for addit	ional det	ails								
Clinical laboratory tests	Х			Х		Х	Х	Х	Х	Х	Х		Х
Cystatin C ¹	Х			Х		Х	Х	Х	Х	Х	Х		Х

Table 1.Schedule of Activities

Visit Identifier	Screen 1	Screen 2	Screen 3	Run-Ir	Baseline ^a	Treat mo	t ment P l orning do ot	hase [all ose of bli herwise	procedur nded IP, noted]	es before unless	Follo	ow-up	Early
Week Relative to Dosing on Day 1				-2	-1	0	1	2	4	6	7-14 days	28-35	Termi
Days Relative to Dosing on Day 1	Visit 1 to ≥ 4	o Visit 4 sl and ≤6 we	nould be eks	-14±2	-4±2	1	5±1	14±2	28±2	42(-3) ^b	post last dose	days post last dose ^c	nation (ET)
Visit to Site or Imaging Facility	1	2	3	4	5	6	7	8	9	10	11		
Serology (HepBsAg, HepBcAb, HCVAb, HCV RNA, HIV), Serum FSH (females only)	Х												
Ceruloplasmin, Coagulation (aPTT, PT, PT/INR), α1-antitrypsin (A1AT)	Х												
CCI													
													┢
Fasting Lipid Panel	Х			X		X	X	X	X	X	х		X
CCI													1
													 
Apolipoproteins (A1, B100 and C3)						Х				Х			
CCI													1
													1
													1
Plasma PCSK9						Х				Х			
OATP Pharmacogenomics blood sample ^o						Х							
Banked bio-specimen: Prep D1.5°						Х							
Banked bio-specimen: Prep B1.5 and B2.5						Х				Х			
Urine Collections													
Urine drug test ^p	Х			Х		Х							
Urinalysis (and microscopy, as appropriate)	Х			Х		Х	Х	Х	Х	Х	Х		Х
Abbreviations: →= ongoing/continuous event; A1AT = CCI EC HCVAb = Hepatitis C Virus Antibody; HCV RNA = H HIV = Human Immunodeficiency Virus; CCI MRI-PDFF = Magnetic Resonance Imaging – Proton II type 9; PE = Physical Examination; CCI PT/INR = Prothrombin Time/International Normalized	= α 1-antitry G = electroc lepatitis C V Density Fat I ; CCI Ratio	psin; AE = cardiogram /irus Ribon Fraction; O	Adverse E ; ET = Ear nucleic Aci ; II OATP = Org	vent; aP ly Termi d; HepB P = Inves ganic An	TT = activa nation; FSI cAb = Hep stigational 1 ion Transp	ated Pa H = Fol atitis B Produc orter P	rtial Thr Ilicle Sti Core A t; IRT = olypepti	ombopla mulating ntibody; Interacti de; PCSI	stin Time Hormon HepBsA ve Respo X9 = Prop	e; BP = B e; CCI g = Hepat nse Techr protein Co	itis B Surfa nology; prvertase Su PT = Pro	re; ce Antigen ıbtilisin/ke: othrombin	; xin Time;

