a. baseline for liver fat assessments by MRI-PDFF is Day -4±2; baseline for all other assessments is Day 1, prior to first dose.

b. The Day 42 visit can occur up to 3 days prior ie, Day 39 to Day 42, but no later than Day 42.

Page 13

- c. To occur via telephone contact and must occur within 28-35 days from administration of the final dose of double-blind IP; this contact can be considered as on-site in order to permit follow-up of open AEs and/or abnormal laboratory tests from prior visit(s), as needed.
- d. Update at post-screening visits.
- e. Assessment to be performed following ≥4-hr fast, at site (as part of site visit) or separate visit(s) to Imaging facility; attempts to be made to perform baseline visit for each assessment (Visit 6 for FibroScan[®] and Visit 5 for MRI-PDFF) within ±2-hr window of initial screen time (Visit 1 for FibroScan[®] and Visit 3 for MRI-PDFF). Post-randomization assessments should be within ±2-hr window of baseline visit time (Visit 6 for FibroScan[®] and Visit 5 for MRI-PDFF).
- f. A single repeat assessment is permitted at screening as determined by sponsor-identified central imaging vendor; at baseline (Visit 5) and at Visit 10, single repeat is permitted only after consultation with the Sponsor.
- g. MRI-PDFF assessment to be performed within approximately 24 hours prior to Visit 10, or on the same day as Visit 10. If subjects perform MRI-PDFF in the morning of same day as Visit 10 visit, they should wait for blood collections before administration of morning dose at the site. Subjects will not take evening dose on Day 42.
- h. MRI-PDFF will be obtained only for those subjects who receive at least 4 weeks of double-blind IP ie for subjects who drop out after Visit 9.
- i. Includes arm and waist circumference, and height at Visit 1 only; targeted PE at Visit 4, Visit 6, Visit 10, Visit 11 and Early Termination; limited PE for follow-up on open AEs/abnormal tests, at investigator discretion.
- j. Visit 4 and Visit 5 reflect single-blind placebo regimen; from Visit 6 onwards, reflects double-blind randomized regimen.

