6.2. Run-in Period (Visit 4)

After the investigator has determined all eligibility criteria have been satisfied (approximately within 1 week following Visit 3), subjects will return to the site after a minimum 8-hour, but preferably 10-hour fast (except water). The single-blind Run-in period will serve to familiarize the subject with the study treatment regimen and exclude subjects who are not compliant with dosing. This visit will occur 14±2 days prior to the planned date of randomization (Visit 6, Day 1).

For all subjects, refer to the Schedule of Activities for the study procedures to be completed at the Run-in visit (Visit 4).

Following completion of the above procedures, single-blind IP will be self-administered (with meal) while witnessed by adequately trained site staff. Subjects will then be discharged from the site with enough IP to last until Day 1 (Visit 6).

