## 7. INTERIM ANALYSES

If, after randomization of approximately 50% subjects of planned number of subjects, a monthly safety review reveals that the study meets one or more criteria listed in Protocol Section 3.3, an interim analysis will be performed in an un-blinded manner by a prespecified IRC, independent from study team.

Before any interim analysis is initiated, the details of the objectives, decision criteria, dissemination plan, and method of maintaining the study blind as per Pfizer's SOPs will be documented and approved in an IRC charter. The analysis details will be documented and approved in an interim analysis SAP or final SAP.

An IA will be conducted after approximately 50% of randomized subjects reach their Week 6 visit (ie, Visit 10 in Schedule of Activities) or drop out of the study before that visit.

The analysis sets for the IA are:

- 1. Safety Analysis Set: All randomized and treated subjects
- 2. Efficacy/PD Analysis Set: All randomized and treated subjects who completed their Week 6 visit (ie, Visit 10 in Schedule of ActivityActivityActivities) or discontinued the study.

For whole liver PDFF, triglycerides (and total cholesterol, HDL-C, direct LDL-C, Total cholesterol/HDL-C ratio, and non HDL-C, AST, ALT, ALP, GGT), the descriptive summarization and inferential statistical analysis (ANCOVA or MMRM) as indicated in Section 6 will be performed using the Efficacy/PD Analysis Set. Standard safety data as described in the IRC Charter will be summarized using the Safety Analysis Set. The figures related to these descriptive and inferential analyses will be using the "Efficacy/PD Analysis Set".

For whole liver PDFF and triglycerides, additional analysis related to predictive probability will be conducted. The Bayesian predictive probability that the following decision critera will be met at the end of the study given the interim data will be calculated using Pfizer internal validated software. The IRC Statistician will utilize the IA outputs (from ANCOVA analysis for whole liver PDFF and MMRM analysis for triglycerides) to compute the predictive probabilities, and will then provide the probability values to the unblinded programmer to be included in the IA table outputs.

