# Safety:

S-C1: At least 95% confident that change from Baseline to Day 42 in triglycerides level with the combination treatment ACC+DGAT is less than the ACC monotherapy treatment

Predictive probability of meeting S-C1 at the end of study, based on interim data, will be computed.

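### The lipid models, and the interim triglyceride criterion S-C1, could adjust for the fasting Visit 4 value as well as Day 1, for a modest possible gain in precision

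*SAP*

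**What the plan says.** SAP 3.3 defines the baseline for the lipid endpoints in the singular: "Baseline is defined as the result closest" before dosing on Day 1. Footnote a to the protocol's Schedule of Activities agrees: "baseline for all other assessments is Day 1, prior to first dose", liver fat by MRI being the only exception.

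The row "Fasting Lipid Panel" in the same schedule is marked at Screen 1, Visit 4 and Visit 6 (Day 1) before active treatment starts. Protocol 6.2 places Visit 4 at 14±2 days before randomization and requires a fast of at least 8 and preferably 10 hours. Protocol 6.4.1 sets the same fast for Day 1.

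SAP Table 3 models the log relative change of each lipid in an MMRM. The terms are treatment, study day, their interaction, the log baseline value and log baseline whole liver PDFF. The Visit 4 lipid value does not appear.

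SAP Section 7 makes one of these models matter at the interim. Criterion S-C1 asks for at least 95% confidence that "change from Baseline to Day 42 in triglycerides level with the combination treatment ACC+DGAT is less than the ACC monotherapy treatment". Its predictive probability takes its inputs "from ANCOVA analysis for whole liver PDFF and MMRM analysis for triglycerides".

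**The concern.** Fasting triglycerides vary within a person from day to day, so one value is an imperfect measure of the subject's usual level. A second pre-randomization value, taken under the same fasting rule, may carry further information about the Day 42 value. The plan collects it and leaves it out of the model without saying why.

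The point reaches a little beyond an exploratory table. S-C1 is one of only two interim predictive-probability criteria. Protocol 1.6.3 says the trial will explore whether PF-06865571 offsets the triglyceride rise seen with PF-05221304. The contrast rests on 28 planned subjects per arm, with about half of them available at the interim. SAP 5.1 allows interim results to inform future study planning or stopping for futility. Residual variance that could be removed lowers the chance of meeting S-C1 when the combination really does lower triglycerides.

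**Working it through.** **The plan's own figure.** Neither document states a power or precision for triglycerides or S-C1. The only stated power is for liver fat, combination against placebo, and it reproduces: ln(0.70) = −0.357; SE = 0.32 × √(1/12 + 1/24) = 0.113; Φ(0.357/0.113 − 1.645) ≈ 93%, against the stated figure of more than 90%. From that section I carry over only the 24 completers per active arm.

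**Set-up.** Let *a* = corr(Day 42, Day 1), *b* = corr(Day 42, Visit 4) and *c* = corr(Visit 4, Day 1), all for log triglycerides. None is given, so each is an assumption. I treat the Day 42 contrast as an ANCOVA and leave out the liver-fat covariate. Residual variance, as a fraction of the total, is:

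- Day 1 only: 1 − a²
- mean of Visit 4 and Day 1: 1 − (a + b)² / [2(1 + c)]
- Day 1 and Visit 4 as two covariates: 1 − (a² + b² − 2abc) / (1 − c²)

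**Equal correlation (a = b = c = r).** Both two-value forms reduce to 1 − 2r²/(1 + r). The ratio to Day 1 only is (1 + 2r)/(1 + r)².

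| r | variance ratio | SE reduction | equivalent extra subjects |
|---|---|---|---|
| 0.5 | 0.889 | 6% | 12% |
| 0.6 | 0.859 | 7% | 16% |
| 0.7 | 0.830 | 9% | 20% |
| 0.8 | 0.802 | 10% | 25% |

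A simulation of the mean form at r = 0.6 with 24 per arm (20,000 runs) gave 0.85.

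**Correlation that decays with time.** Visit 4 is about eight weeks before Day 42, and Day 1 about six.

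| a, b, c | mean of two | two covariates |
|---|---|---|
| 0.6, 0.55, 0.65 | 0.936 | 0.931 |
| 0.6, 0.5, 0.7 | 1.006 | 0.980 |
| autoregressive, a = 0.6 | 1.045 | 1.000 |

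In the last row, c = 0.6^(14/41) = 0.840 and b = a × c = 0.504. For autoregressive decay with a from 0.5 to 0.8, the mean form runs from 1.035 to 1.065, while the covariate form stays at 1.000.

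**Cost of the extra covariate.** Roughly one over the residual degrees of freedom. With 84 completers, four arms and two existing covariates, that is 1/(84 − 6) = 1.3%. With half as many at the interim, it is 1/(42 − 6) = 2.8%.

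**Effect on S-C1.** I assume a total log SD of 0.5 and a true combination/PF-05221304 ratio of 0.80; for the predictive probability, the interim ratio observed is also 0.80. Equal correlation is used, so these are best cases.

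| r | residual SD | chance of meeting S-C1 at study end, 24 per arm | SAP 9.2 predictive probability, 14 of 28 per arm |
|---|---|---|---|
| 0.5 | 0.433 → 0.408 | 56% → 60% | 0.61 → 0.66 |
| 0.6 | 0.400 → 0.371 | 61% → 67% | 0.67 → 0.73 |
| 0.7 | 0.357 → 0.325 | 70% → 77% | 0.76 → 0.82 |
| 0.8 | 0.300 → 0.269 | 82% → 89% | 0.87 → 0.93 |

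**Direction of the effect.** In the SAP 9.2 code at 14 of 28 per arm, the final-analysis SE and the predictive SD are both 0.267σ. The formula therefore reduces to Φ(−1.645 − d/(0.267σ)), with d the observed log difference. As σ grows this tends to Φ(−1.645) = 0.05. At an observed ratio of 0.90, raising σ from 0.371 to 0.400 moves it from 0.280 to 0.255.

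**The case against.** The strongest reply is that nothing here is wrong. Protocol and SAP agree on a Day 1 baseline, the other laboratory data follow the same rule, and the arm comparison is unbiased. The lipid analyses are tertiary, protocol 1.6.3 speaks only of exploring the triglyceride effect, and the SAP sets no predictive-probability threshold for S-C1. All of that stands, and it limits the point to an optional improvement.

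The reply also says that averaging visits creates a second triglyceride baseline beside the one in the safety tables, and may add variance. That is a sound objection to averaging. It does not touch a second covariate, which leaves the Day 1 baseline as it is.

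A reader might infer three stronger things that the documents do not support:

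- **That Day 1 variation passes in full into each change score.** The model already has log baseline as a covariate, so subtracting baseline in the response does not alter the treatment contrast. Only the smaller gain computed above is available.
- **That a noisier baseline draws the predictive probability toward one half.** Under the SAP 9.2 code at half information it moves toward 0.05.
- **That an 11% to 20% gain is assured.** It needs Visit 4 to predict Day 42 as well as Day 1 does, which the documents cannot show.

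**Conclusion.** The point holds as a modest loss of precision. It is neither an error nor a source of bias. The triglyceride model behind S-C1 adjusts for one pre-dose lipid value when two comparable ones are collected, and the second is known before randomization.

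The size cannot be fixed from the documents. Before the small degree-of-freedom cost, the variance reduction runs from about none under autoregressive decay to 11–20% under equal visit correlation of 0.5 to 0.8. In the intermediate examples it is 2% and 7%. At the interim, a 2% gain would be cancelled by the lost degree of freedom. The S-C1 figures also depend on the assumed log SD of 0.5 and ratio of 0.80.

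Visit 4 precedes the placebo run-in, so its mean may differ from Day 1. As a pre-randomization covariate, it cannot bias the comparison between arms.

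**What to change.** In SAP Table 3, keep Day 1 as the baseline for the relative change and add log(Visit 4 value) as a second covariate in the triglyceride and other lipid MMRMs. State in Section 7 that the same model feeds S-C1. Do not substitute the simple mean of Visit 4 and Visit 6 for the baseline.

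Add a simple rule for a missing Visit 4 value that ignores treatment arm, for example using the subject's own Day 1 value. If Day 1 is missing, the existing closest-prior rule already makes Visit 4 the baseline; the two covariates then coincide for that subject, and the SAP should say this is accepted.

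The change must be fixed before anyone sees unblinded interim data. It costs one SAP line, one derivation and one degree of freedom, with no new visit or blood draw. If the sponsor prefers the present model, one sentence of justification would be enough.

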# 3.4. Baseline Variables

Baseline variables are those collected on Day 1, prior to dosing, or before Day 1. The demographic data of age, race, weight, height, and body mass index will be summarized by sex at birth and treatment in accordance with the sponsor reporting standards. In addition, the demographic data will be summarized by treatment only in accordance with the sponsor reporting standards. The number and proportion of subjects enrolled in each study site will also be presented.

Subjects will be stratified at randomization (Day 1) by the MRI-PDFF liver fat measurement determined by the Sponsor-identified central imaging vendor of images obtained during Screen 3:

- Screening liver fat  $\geq 8\%$  and <15%;
- Screening liver fat  $\geq 15\%$ ;
- Subjects will then be stratified by the presence or absence of type 2 diabetes mellitus (T2DM).

For Baseline diabetic status, data will be obtained from the case report forms (CRFs). Screening liver fat was used as a binary variable for stratification purposes but Baseline liver fat will be used as a continuous covariate in the efficacy analysis to maximize the utility of information. Baseline diabetic status will only be included as a covariate in the primary analysis (analysis of covariance [ANCOVA]) if at least 1/3 of the subjects have T2DM.

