4.3. Randomization Criteria

On Day 1, interactive response technology (IRT) will be used to assign each eligible subject a randomization number, with this number recorded on the electronic Case Report Form (CRF). A computer-generated randomization code using the method of random permuted blocks will be utilized to randomize subjects in 1:2:2:2 ratio

(placebo:PF-05221304:PF-06865571:PF-05221304 plus PF-06865571 combination) prior to the first dose of IP, provided subjects satisfy all of the eligibility criteria outlined in Section 4.1 and Section 4.2.

- An attempt will be made to equally balance the number of subjects assigned to each treatment arm within stratum by utilizing a stratification scheme as follows. Subjects will be stratified at randomization (Day 1) by the MRI-PDFF liver fat measurement determined by the Sponsor-identified central imaging vendor of images obtained during Screen 3:
 - Screening liver fat $\ge 8\%$ and <15%;
 - Screening liver fat $\geq 15\%$;
 - Subjects will then be stratified by the presence or absence of T2DM.

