9.2. Analysis of the Primary Endpoint

The analysis population for primary endpoint analyses will include all randomized subjects who received at least 1 dose of IP (Full Analysis set).

The primary endpoint will be the relative change from baseline to Day 42 in whole liver PDFF. Baseline will be the closest measurement prior to first dose on Day 1. An analysis of covariance (ANCOVA) will be performed on log-transformed relative change from baseline with treatment and baseline diabetes as factors, and log-transformed baseline whole liver PDFF value as a covariate. Estimates of the mean relative changes between placebo and each active drug arm (PF-05221304 monotherapy, PF-06865571 monotherapy and PF-05221304 plus PF-06865571 combination) at Day 42, and the corresponding 90% confidence interval (CI) will be obtained from the model. Similarly, PF-05221304 plus PF-06865571 combination will be compared to each monotherapy through estimates of the mean relative change and corresponding 50% and 90% confidence intervals. No adjustment for multiple comparisons will be made. If the model does not fit the data group medians and their differences from the placebo median will be presented. The details will be provided in the SAP.

Descriptive summaries of the observed values and percent change from baseline in whole liver PDFF for each treatment group will also be produced.

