#### 6. ANALYSES AND SUMMARIES

#### 6.1. Primary Endpoint: Whole Liver PDFF

Primary Analysis

- Analysis endpoint: Whole liver PDFF
- Analysis time points: Day 42
- Analysis population: Full Analysis set
- Analysis methodology: Natural log-transformed individual relative change (RC) from Baseline to Day 42 in whole liver PDFF will be analyzed using the ANCOVA. The model will include natural log-transformed Baseline whole liver PDFF. Baseline diabetes status will be included as a covariate only if at least 1/3 of the subjects have T2DM.

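### Should the primary ANCOVA also adjust for the Screen 3 liver fat value that set the randomisation stratum?

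*SAP*

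**What the plan says.** Protocol 4.3 sets the first stratification factor: "Subjects will be stratified at randomization (Day 1) by the MRI-PDFF liver fat measurement determined by the Sponsor-identified central imaging vendor", using the Screen 3 images and a cut at 15%. Type 2 diabetes is the second factor.

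The baseline for the endpoint is a different scan, Visit 5 on Day -4±2 (Schedule of Activities, footnote a). Protocol 9.2 models the log relative change with "treatment and baseline diabetes as factors, and log-transformed baseline whole liver PDFF value as a covariate". SAP 6.1 agrees on the liver fat term: "The model will include natural log-transformed Baseline whole liver PDFF". It adds diabetes "only if at least 1/3 of the subjects have T2DM".

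SAP 3.4 explains how the two scans are used: "Screening liver fat was used as a binary variable for stratification purposes but Baseline liver fat will be used as a continuous covariate". The reason it gives is to get the most information out of the measurement. Beyond eligibility and stratification, Screen 3 fat appears in the baseline summary of stratification factors (SAP 6.5) and in an optional subset analysis (SAP 6.4).

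**The concern.** Two ordinary instincts point the same way. First, a factor used to stratify randomisation normally appears in the analysis model. If it predicts outcome and is left out, standard errors can be larger than they need be. Second, Visit 5 is both a covariate and the denominator of the endpoint, so its scan error enters every subject's log relative change. Screen 3 is a second pre-randomisation reading of the same quantity, already held for each subject, and could in principle remove part of that error.

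The precision of all five primary contrasts would be at stake. It matters most for the combination against each monotherapy, which is reported with 50% and 90% intervals and planned on 24 completers per arm.

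**Working it through.** **1. The plan's own power.** Inputs from Protocol 9.1: a 30% relative reduction, SD 0.32 on the log relative change, 12 and 24 completers, 1-sided 0.05.

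- SE = 0.32 × √(1/12 + 1/24) = 0.1131.
- |ln 0.70| / SE = 0.3567 / 0.1131 = 3.153.
- Power = Φ(3.153 - 1.645) = 93.4%, against the stated figure of more than 90%.

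So the stated power is met without a second liver fat covariate.

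**2. What Screen 3 could add.** Write the subject's underlying log liver fat with between-subject variance B, Visit 5 and Day 42 scan-error variance e², drift variance d² between Screen 3 and Visit 5, and Screen 3 error SD k times that of Visit 5. Let R = 0.1024 - 2e², so that the log relative change keeps the planned variance 0.32² = 0.1024.

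- Residual variance given Visit 5: B + R + e² - B²/(B + e²).
- Residual variance given both scans: B + R + e² - c′V⁻¹c, with c = (B, B) and V = [[B + e², B], [B, B + d² + k²e²]].
- Cost of one more degree of freedom with 84 completers: (84 - 6)/(84 - 7) = 78/77 = 1.013. Without the diabetes term it is 79/78, also 1.013.

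The documents give none of e, d, k or B. All are assumptions, with √B = 0.45. Some drift is plausible. Visit 4 follows Visit 3 "approximately within 1 week following Visit 3" and falls on Day -16 to -12, and Visit 5 falls on Day -6 to -2. The scans are therefore about 6 to 21 days apart, with the placebo run-in starting between them. A larger Screen 3 error is also plausible, because segment matching covers only Baseline and later scans: "the same segments are to be used at both Baseline and post-Baseline time points in the calculation of whole liver PDFF".

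Worked case, e = 0.10, d = 0.10, k = 1 (B = 0.2025, R = 0.0824):

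- Given Visit 5: 0.2949 - 0.2025²/0.2125 = 0.1019.
- Given both: 0.2949 - 0.1960 = 0.0989.
- Ratio 0.970 × 1.013 = 0.982, a change of -1.8%.

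Change in contrast variance (%), by log scan-error SD:

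| Scenario | 0.03 | 0.05 | 0.08 | 0.10 | 0.15 | 0.20 | Break-even SD |
|---|---|---|---|---|---|---|---|
| d 0.10, k 1 | +1.2 | +0.9 | -0.4 | -1.8 | -6.6 | -12.8 | 0.073 |
| d 0.15, k 1 | +1.3 | +1.1 | +0.2 | -0.8 | -5.1 | -11.0 | 0.085 |
| d 0.10, k 1.5 | +1.2 | +1.0 | +0.1 | -0.8 | -3.8 | -7.5 | 0.081 |
| d 0, k 1 (favourable) | +0.9 | +0.1 | -1.7 | -3.3 | -8.4 | -14.8 | 0.052 |

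The two right-hand SDs are hard to square with the plan. Two scans' error would take 2 × 0.15²/0.1024 = 44%, or 2 × 0.20²/0.1024 = 78%, of the whole planned variance.

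**3. What that means for intervals and power.** With drift and a scan-error SD of 0.10 or less, variance changes by +1.3% to -1.8%. Interval width then changes by √1.013 - 1 = +0.6% to √0.982 - 1 = -0.9%. Power against placebo lies between 93.2% and 93.8%. Starting from the stated power of about 90% at 1-sided 0.25, combination versus monotherapy lies between 89.8% and 90.3%.

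**4. The interim.** SAP 7 uses the same ANCOVA at about half the subjects, roughly 42 completers. The degree of freedom then costs 36/35 = 1.029. Break-even rises to 0.097 (d 0.10, k 1), or 0.113 with k 1.5. Below that the extra term adds noise, on average, to the inputs of the predictive probability (SAP 9.2).

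**5. Simulation check of validity.** Trials were simulated with 84 completers, Screen 3 of at least 8%, blocks of 7 within the 15% strata, 4,000 runs per scenario and no diabetes term.

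- The mean contrast lay between -0.355 and -0.359 with or without Screen 3, against a true ln 0.70 = -0.357.
- The planned model's SE was close to the actual spread of its estimates: from 0.1131 against 0.1145 to 0.1016 against 0.0992.
- Adding the continuous Screen 3 value multiplied the SE by 1.006 if it carried nothing beyond Visit 5, by 0.994 to 0.995 if 10% of the change variance was visit noise, and by 0.95 to 0.96 at 50%.
- The SE rose in 79% of trials in the first case and in 47% to 48% in the second.
- Adding the binary stratum instead gave ratios of 0.96 to 1.004.

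**The case for a change.** The strongest case for the extra term runs as follows. The reason in SAP 3.4 justifies a continuous value over a binary stratum, but does not address a second scan. The average cost at the final analysis is capped at about 1.3% of variance. The gain could reach 5% to 7% if the scan-error SD were 0.15 with equal scan errors. Protocol 1.6.2 itself cites measurement variability when it sets the 8% entry threshold, and no new data are needed.

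The first point stands as a reading of SAP 3.4: the plan does not discuss a second covariate. The arithmetic also stands. It does not show an improvement, for three reasons.

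- The design works against large scan error, though it does not quantify it. Whole-liver PDFF averages at least 5 of 9 segments, matched between Baseline and Day 42 (SAP 3.1). Scans are fasted and held to a ±2-hour clock window (Protocol 1.6.1). As far as practical, one blinded central reader analyses them (Protocol 7.1.2).
- The 1.3% is an average. In a further simulation with simple randomisation and drift 0.10, contrast variance rose in about 79%, 73%, 56% and 44% of trials at scan-error SDs of 0.03, 0.05, 0.08 and 0.10. The worst 5% of trials lost at least 4% to 5.5%.
- The change is not free. It would need a protocol amendment to the primary model in a sponsor-open trial, a segment rule for Screen 3, a rule for repeats ("A single repeat assessment is permitted at screening as determined by sponsor-identified central imaging vendor"), a rule for a missing Screen 3 value, and a statement of the interim model. Losing one completer to a missing value costs about 84/83 - 1 = 1.2% of variance, as much as the likely gain.

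**Conclusion.** The concern does not hold. The omission is real, but it is a stated choice, and the planned ANCOVA is valid and unbiased, with standard errors that match the spread of its estimates closely. The plan's power is reproduced at 93.4% without the extra term. With drift of 0.10 to 0.15 and a scan-error SD of 0.10 or less, adding log Screen 3 PDFF changes contrast variance by between +1.3% and -1.8%, a range that includes zero. At the interim it is a loss, on average, below an SD of about 0.10. Larger gains appear only where scan error takes up 44% or more of the planned variance.

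These sizes rest on assumed scan-error, drift and between-subject SDs. A sponsor holding repeatability data that showed large scan error could reasonably choose the extra covariate. Nothing in the documents shows that it should, so this is a preference between two sound models.
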